#### ***Serious Adverse Event***

Adverse events are classified as serious or non-serious.

A ***serious adverse event*** is any AE that is:

- fatal
- life-threatening
- requires or prolongs hospital stay
- results in persistent or significant disability or incapacity
- a congenital anomaly or birth defect
- an important medical event

Important medical events are those that may not be immediately life threatening, but are clearly of major clinical significance. They may jeopardize the subject, and may require intervention to prevent one of the other serious outcomes noted above. For example, drug overdose or abuse, a seizure that did not result in in-patient hospitalization, or intensive treatment of bronchospasm in an emergency department would typically be considered serious.

All adverse events that do not meet any of the criteria for serious should be regarded as ***non-serious adverse events***.

#### ***Adverse Event Reporting Period***

The study period during which adverse events must be reported is normally defined as the period from the initiation of any study procedures to the end of the study treatment follow-up. For this study, the study treatment follow-up is defined as 30 days following the last administration of study treatment.

### ***Preexisting Condition***

A preexisting condition is one that is present at the start of the study. A preexisting condition should be recorded as an adverse event if the frequency, intensity, or the character of the condition worsens during the study period.

### ***General Physical Examination Findings***

At screening, any clinically significant abnormality should be recorded as a preexisting condition. At the end of the study, any new clinically significant findings/abnormalities that meet the definition of an adverse event will be recorded and documented as an adverse event.

### ***Post-study Adverse Event***

All unresolved adverse events will be followed by the investigator until the events are resolved, the subject is lost to follow-up, or the adverse event is otherwise explained. At the last scheduled visit, the investigator will instruct each subject to report any subsequent event(s) that the subject, or the subject's personal physician, believes might reasonably be related to participation in this study. The investigator will notify the sponsor of any death or adverse event occurring at any time after a subject has discontinued or terminated study participation that may reasonably be related to this study. The sponsor will also be notified if the investigator should become aware of the development of cancer or of a congenital anomaly in a subsequently conceived offspring of a subject that has participated in this study.

### ***Abnormal Laboratory Values***

A clinical laboratory abnormality should be documented as an adverse event if any one of the following conditions is met:

- The laboratory abnormality is not otherwise refuted by a repeat test to confirm the abnormality
- The abnormality suggests a disease and/or organ toxicity
- The abnormality is of a degree that requires active management; e.g. change of dose, discontinuation of the drug, more frequent follow-up assessments, further diagnostic investigation, etc.

### ***Hospitalization, Prolonged Hospitalization or Surgery***

Any adverse event that results in hospitalization or prolonged hospitalization should be documented and reported as a serious adverse event unless specifically instructed otherwise in this protocol. Any condition responsible for surgery should be documented as an adverse event if the condition meets the criteria for and adverse event.

Neither the condition, hospitalization, prolonged hospitalization, nor surgery are reported as an adverse event in the following circumstances:

- Hospitalization or prolonged hospitalization for diagnostic or elective surgical procedures for a preexisting condition. Surgery should **not** be

- reported as an outcome of an adverse event if the purpose of the surgery was elective or diagnostic and the outcome was uneventful.
- Hospitalization or prolonged hospitalization required to allow efficacy measurement for the study.
  - Hospitalization or prolonged hospitalization for therapy of the target disease of the study, unless it is a worsening or increase in frequency of hospital admissions as judged by the clinical investigator.

## **8.2 Recording of Adverse Events**

At each contact with the subject, the investigator will seek information on adverse events by specific questioning and, as appropriate, by examination. Information on all adverse events will be recorded immediately in the source document, and also in the appropriate adverse event module of the case report form (CRF). All clearly related signs, symptoms, and abnormal diagnostic procedures results should be recorded in the source document, though should be grouped under one diagnosis.

All adverse events occurring during the study period will be recorded.

The clinical course of each event will be followed until resolution, stabilization, or until it has been determined that the study treatment or participation is not the cause. Serious adverse events that are still ongoing at the end of the study period will be followed up to determine the final outcome. Any serious adverse event that occurs after the study period and is considered to be possibly related to the study treatment or study participation will be recorded and reported immediately.

## **8.3 Unblinding Procedures:**

At the completion of the accrual period subjects will remain blinded until after the primary and secondary endpoints have been collected.

## **8.4 Stopping Rules:**

Grade 4 toxicity (probably or definitely drug related): Treatment will be discontinued definitively.

Participants will be discontinued from study drug as per physician discretion

## **8.5 Data and Safety Monitoring Plan**

The safety monitoring will include careful assessment and appropriate reporting of adverse events as noted above, as well as the compliance and implementation of the SKCC data and safety-monitoring plan. Medical monitoring will include a regular assessment of the number and type of serious adverse events by both the PI and the SKCC DSMC.

### 8.5.1 Medical Monitoring and AE/SAE Reporting

Every SKCC investigator initiated protocol includes requirements for reporting of adverse events based on CTC 4.0. All events are reported to the IRB and Medical Monitor using a password protected web-site. In addition all unexpected and serious adverse events (SAEs) are reported to the TJU IRB and to the Food and Drug Administration (FDA) if applicable. The investigator is required to submit all unexpected and serious adverse events to the TJU IRB and the Medical Monitor within the timeframes outlined in the below table. All AE/SAEs will be reported to the DSMC at the quarterly DSMC review meetings. **Fatal adverse events related to treatment which are unexpected must be reported within 24 hours to the TJU IRB and the DSMC. Fatalities not related to the study drug/device must be reported within 5 days**

A summary of the reporting requirements for SKCC investigator-initiated studies are presented below.

|                            | Grade 1  | Grade 2  |  | Grade 3                   |  |                            |  | Grades 4 and 5   |
|----------------------------|--|--|--|---------------------------|--|----------------------------|--|--|
|                            | Unexpected and Expected                                  | Unexpected   | Expected   | Unexpected                |  | Expected                   |  | Unexpected and Expected  |
|                            |  |  |  | With Hospitalization      | Without Hospitalization                                  | With Hospitalization       | Without Hospitalization                                  |  |
| Unrelated Unlikely         | Reviewed at Quarterly DSMC Meeting and IRB Annual Review | Reviewed at Quarterly DSMC Meeting and IRB Annual Review | Reviewed at Quarterly DSMC Meeting and IRB Annual Review | 5 Working Days            | Reviewed at Quarterly DSMC Meeting and IRB Annual Review | 5 Working Days             | Reviewed at Quarterly DSMC Meeting and IRB Annual Review | Phase 1 - 48 Hours (Death: 24 Hours)
Phase 2 - 5 Working Days |
| Possible Probable Definite | Reviewed at Quarterly DSMC Meeting and IRB Annual Review | Reviewed at Quarterly DSMC Meeting and IRB Annual Review | Reviewed at Quarterly DSMC Meeting and IRB Annual Review | 48 Hour (Death: 24 Hours) | Phase 1 - 48 Hours
Phase 2 - 5 Working Days           | 48 Hours (Death: 24 Hours) | Reviewed at Quarterly DSMC Meeting and IRB Annual Review | Phase 1 and Phase 2 - 48 Hours (Death: 24 Hours)                 |

**\*\*NOTE: This table is based on the NCI AE/SAE reporting Guidelines and the TJU IRB Policy and Procedures. Please follow the individual protocol AE/SAE reporting guidelines if more stringent reporting procedures are specified\*\***

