### 8.5.2 Data and Safety Monitoring Committee

Data and Safety Monitoring Committee (DSMC) is the Data and Safety Monitoring Board (DSMB) for the SKCC. The DSMC is a multidisciplinary committee charged with overseeing the monitoring of safety of participants in clinical trials, and the conduct, progress, validity, and integrity of the data for all clinical trials at the Thomas Jefferson University SKCC. The committee meets

quarterly to review the progress and safety of all active research protocols that are not monitored by another safety and data monitoring committee or board.

- The DSMC meets quarterly. Additional DSMC meetings are scheduled based on the nature and number of trials being monitored over a specified time period. The DSMC meets (by conference call) within 24 hours following the notification of an unexpected adverse event felt to be related to the study drug.
- Prior to each DSMC meeting, each board member, is provided a printout of all reported AEs and SAEs occurring during the reporting period for this clinical trial. The principal investigator provides a detailed and comprehensive narrative assessment of current adverse events to date, indicating their possible significance and whether these toxicities have affected the conduct of the trial. DSMC members are provided with the principal investigator's assessment, a written report summarizing adverse events, safety data, and activity data observed during the specified time period described in each protocol, as well as recommendations from the Medical Monitor. A review of outcome results (response, toxicity and adverse events) and factors external to the study (such as scientific or therapeutic developments) is discussed, and the Committee votes on the status of each study.
- A summary of the board's action is sent to each investigator, the PRC and TJU IRBs. The DSMC actions may include recommendations/requirements that will lead to improved patient safety and/or efficacy, significant benefits or risks that have developed, or other changes determined to be necessary. The DSMC may also take note of slow accrual or lack of scientific progress, and refer such issues to the PRC. The DSMC provides the investigator with the rationale for any decision made.

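### The adverse-event reporting table sets no expedited timeframe for serious events of grade 1 or 2, and no rule assures that the DSMC hears of them before its quarterly meeting

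*Combined protocol and SAP*

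**What the plan says.** Section 8.1 makes an event serious by outcome. One criterion is that it "requires or prolongs hospital stay"; another is that it is an important medical event. Grade plays no part. The hospitalization paragraph of the same section adds: "Any adverse event that results in hospitalization or prolonged hospitalization should be documented and reported as a serious adverse event", subject to listed exceptions such as elective procedures for a pre-existing condition.

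Section 8.5.1 handles timing. Investigators are "required to submit all unexpected and serious adverse events to the TJU IRB and the Medical Monitor within the timeframes outlined in the below table". The same paragraph sends all events to the IRB and Medical Monitor through a web-site, without a deadline, and sends all AEs and SAEs to the DSMC at its quarterly meetings. In the table, every grade 1 and grade 2 cell reads "Reviewed at Quarterly DSMC Meeting and IRB Annual Review". A note under the table gives way to stricter protocol rules where these exist.

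Section 8.5.2 has the DSMC meet by conference call "within 24 hours following the notification of an unexpected adverse event felt to be related to the study drug", with no limit by grade. Section 2.5 requires immediate notice to the DSMB and IRB for grade 3 or 4 SAEs; section 8.5.2 identifies the DSMB with the DSMC. Section 8.2 says that an SAE arising after the study period and "considered to be possibly related to the study treatment or study participation will be recorded and reported immediately".

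**The concern.** Seriousness and grade are different scales. Section 8.1 uses the first to decide what is serious, and the section 8.5.1 table uses the second to decide how fast it is reported. The table brings in hospitalization, the commonest bridge between the two, only at grade 3. A grade 2 event that puts a patient in hospital is serious by definition, but it has the same timetable as a trivial grade 1 event.

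Safety and tolerability of metformin is a secondary objective, and the DSMC and IRB are the bodies charged with overseeing it. If staff follow the table, an unexpected drug-related hospitalization graded 2 need not reach the DSMC until the next quarterly meeting. Recruitment and dosing continue in the meantime.

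**Working it through.** The plan gives no figure to reproduce, so the check is a cell-by-cell reading, followed by a search for any other timed rule.

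**1. The table (section 8.5.1)**

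| Event | Unrelated / unlikely | Possible / probable / definite |
|---|---|---|
| Grade 1 | quarterly DSMC, annual IRB | quarterly DSMC, annual IRB |
| Grade 2, unexpected | quarterly DSMC, annual IRB | quarterly DSMC, annual IRB |
| Grade 2, expected | quarterly DSMC, annual IRB | quarterly DSMC, annual IRB |
| Grade 3 with hospitalization, expected or unexpected | 5 working days | 48 hours (24 if fatal) |

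There are 3 grade 1–2 categories × 2 relatedness rows = 6 cells. Cells with a seriousness or hospitalization split: 0 of 6. The two grade 3 with-hospitalization timeframes do not depend on the Phase 1/Phase 2 distinction used elsewhere in the table, so the comparison does not turn on how a pilot study is classed.

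**2. Does a stricter rule elsewhere apply?** The test case is an on-study, unexpected, drug-related grade 2 event with hospitalization.

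| Rule | Covers | Reaches the test case? |
|---|---|---|
| Section 2.5, immediate notice | grade 3 or 4 SAEs | No |
| Section 8.5.1, 24 hours or 5 days | deaths | No |
| Section 8.2, immediate reporting | possibly related SAEs after the study period | No; this one is on study |
| Section 8.5.1, web-site route to IRB and Medical Monitor | all events | Yes, but no deadline, and the DSMC is not named |

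Timed rules that shorten the table's timeframe for this event: 0. The note under the table therefore has nothing to defer to. The reporting sentence in section 8.5.1 could mean events that are both unexpected and serious, or events that are either; the test case falls under it both ways.

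**3. The 24-hour DSMC call.** Its clock starts at notification. For the test case, the only notification to the DSMC that the plan requires is the quarterly one. The call follows promptly only if someone chooses to notify earlier.

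**4. Size of the wait**

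- DSMC: up to one quarter, 52 / 4 = 13 weeks. Planned exposure is 8–10 weeks and at most 12 (section 1.6). Since 13 > 12, a patient's entire treatment can fit between two meetings.
- IRB: the only timed entry is annual review, up to about 12 months.
- Accrual in the meantime: 50 patients over 24 months (section 3.1) is 24 / 3 = 8 quarters, and 50 / 8 = 6.25, or about 6 more patients per quarter, assuming even accrual.

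**The case against.** A reader might infer several stronger things that the documents do not support.

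- *That the IRB learns of such an event only at annual review.* Section 8.5.1 also sends all events to the IRB and Medical Monitor through the web-site. What is missing is a deadline, not a route.
- *That the 24-hour DSMC call can never be triggered.* It can. Grade 3–4 SAEs go to the DSMC immediately under section 2.5, and unexpected treatment-related deaths within 24 hours under section 8.5.1. At grades 1–2 nothing bars earlier notice; it is simply not required.
- *That sections 8.5.1 and 8.5.2 contradict each other.* One sets when the DSMC is told and the other how soon it meets once told. Both can be obeyed. They are misaligned.
- *That section 8.2 proves a stricter deadline after the study than during it.* Its immediate-reporting sentence names no recipient, so it is not a like-for-like IRB or DSMC deadline.

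Other objections bear on weight. The table is a summary resting on NCI guidelines, IRB policy and the cancer center's monitoring plan, which are not reproduced and might close the gap. The CTCAE grade definitions are not reproduced either, so the documents cannot show how often a hospitalized event would be graded 1 or 2. The 48-hour comparison sets events of different severity side by side. Patients are also protected day to day by weekly calls, toxicity rules and physician discretion, none of which waits for a committee.

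These points limit the consequences. They do not supply a timeframe: within the protocol, which is what site staff will follow, a serious grade 1–2 event still has none that is expedited.

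**Conclusion.** The gap is real but narrow. Quarterly DSMC and annual IRB review are the only stated timeframes for an on-study grade 1–2 SAE, including a related one with hospitalization, and the 24-hour DSMC call is not assured for it. In the worst case the DSMC hears about 3 months later.

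This rests on the protocol text alone, and on reading the study period in section 8.2 as the reporting period in section 8.1, which ends 30 days after the last dose. The frequency of such events is unknown and probably small. The primary analysis is unaffected. The point concerns oversight of a stated secondary objective and should be corrected because the correction is cheap.

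**What to change.** Add to section 8.5.1, in words such as:

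> Any grade 1 or 2 event that meets the section 8.1 definition of serious is reported to the IRB and Medical Monitor on the table's existing timeframes for grade 3 with hospitalization: 48 hours if possibly, probably or definitely related; 5 working days if unrelated or unlikely. If the event is unexpected and related, the DSMC is notified at the same time as the IRB.

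Keep the addition to grades 1 and 2. Applying those timeframes to SAEs of every grade would loosen existing rules: the 48-hour Phase 1 entry for unrelated grade 4–5 events, the 24-hour entries for deaths, and immediate notice under section 2.5. Leave those rules as they are. Leave the scope of the 24-hour call in section 8.5.2 unchanged too, since limiting it to SAEs would weaken a safeguard that now covers any unexpected related event. Then reconcile sections 8.5.1, 8.5.2, 2.5 and 8.2, and name the recipient of the immediate report in section 8.2.

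The cost is a short amendment and a few more expedited reports. The note under the table already allows stricter protocol-specific reporting, and the DSMC's own procedures need not change.

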### 8.5.2 Data and Safety Monitoring Committee

Data and Safety Monitoring Committee (DSMC) is the Data and Safety Monitoring Board (DSMB) for the SKCC. The DSMC is a multidisciplinary committee charged with overseeing the monitoring of safety of participants in clinical trials, and the conduct, progress, validity, and integrity of the data for all clinical trials at the Thomas Jefferson University SKCC. The committee meets

quarterly to review the progress and safety of all active research protocols that are not monitored by another safety and data monitoring committee or board.

- The DSMC meets quarterly. Additional DSMC meetings are scheduled based on the nature and number of trials being monitored over a specified time period. The DSMC meets (by conference call) within 24 hours following the notification of an unexpected adverse event felt to be related to the study drug.
- Prior to each DSMC meeting, each board member, is provided a printout of all reported AEs and SAEs occurring during the reporting period for this clinical trial. The principal investigator provides a detailed and comprehensive narrative assessment of current adverse events to date, indicating their possible significance and whether these toxicities have affected the conduct of the trial. DSMC members are provided with the principal investigator's assessment, a written report summarizing adverse events, safety data, and activity data observed during the specified time period described in each protocol, as well as recommendations from the Medical Monitor. A review of outcome results (response, toxicity and adverse events) and factors external to the study (such as scientific or therapeutic developments) is discussed, and the Committee votes on the status of each study.
- A summary of the board's action is sent to each investigator, the PRC and TJU IRBs. The DSMC actions may include recommendations/requirements that will lead to improved patient safety and/or efficacy, significant benefits or risks that have developed, or other changes determined to be necessary. The DSMC may also take note of slow accrual or lack of scientific progress, and refer such issues to the PRC. The DSMC provides the investigator with the rationale for any decision made.

## **9.0 DATA HANDLING AND RECORD KEEPING**

### **9.1 Confidentiality**

Information about study subjects will be kept confidential and managed according to the requirements of the Health Insurance Portability and Accountability Act of 1996 (HIPAA). Those regulations require a signed subject authorization informing the subject of the following:

- What protected health information (PHI) will be collected from subjects in this study
- Who will have access to that information and why
- Who will use or disclose that information
- The rights of a research subject to revoke their authorization for use of their PHI.

In the event that a subject revokes authorization to collect or use PHI, the investigator, by regulation, retains the ability to use all information collected prior to the revocation of subject authorization. For subjects that have revoked authorization to collect or use PHI, attempts should be made to obtain permission to collect at least vital status (i.e. that the subject is alive) at the end of their scheduled study period.

## **9.2 Source Documents**

Source data is all information, original records of clinical findings, observations, or other activities in a clinical trial necessary for the reconstruction and evaluation of the trial. Source data are contained in source documents. The source documents for the trial will include: hospital records, clinical and office charts, laboratory notes, pharmacy dispensing records, pathology records, adverse events and SAE forms, phone interview logs.

## **9.3 Case Report Forms**

The study case report form (CRF) is the primary data collection instrument for the study. All data requested on the CRF must be recorded. All missing data must be explained. If a space on the CRF is left blank because the procedure was not done or the question was not asked, write "N/D". If the item is not applicable to the individual case, write "N/A". All entries should be printed legibly in black ink. If any entry error has been made, to correct such an error, draw a single straight line through the incorrect entry and enter the correct data above it. All such changes must be initialed and dated. DO NOT ERASE OR WHITE OUT ERRORS. For clarification of illegible or uncertain entries, print the clarification above the item, then initial and date it.

